6.1 Site Selection

The study sponsor has overall responsibility for site and investigator selection.

6.1.1 Study Setting

This is a multicentre study that will be carried out in the Fetal Medicine Units in the UK (that are within the FMF Research Network).

6.1.2 Site/Investigator Eligibility Criteria

Once a site has been assessed as being suitable to participate in the study, the study team will provide them with a copy of this protocol and relevant study documents.

To participate in the SPREE study, investigators and study sites must fulfil a set of criteria that have been agreed by the SPREE Study Management Group (SMG) and that are defined below.

Study sites meeting eligibility criteria and that are accepted by the SMG as being suitable to recruit to the study, will be issued with the SPREE Study Master File (SMF) documentation to use when applying for Site-Specific Approval (SSA).

6.1.2.1 Principal Investigator's (PI) Qualifications and Agreements

The investigator(s) must be willing to sign a UCL CCTU Clinical Study Site Agreement or an Investigator Agreement to comply with the study protocol (confirming their specific roles and responsibilities relating to the study, and that their site is willing and able to comply with the requirements of the study). This includes confirmation of appropriate qualifications, agreement to comply with the principles of GCP, to permit monitoring and audit as necessary at the site, and to maintain documented evidence of all staff at the site who have been delegated significant study related duties.

6.1.2.2 Resourcing at site

The investigator(s) should be able to demonstrate a potential for recruiting the required number of suitable participants within the agreed recruitment period (i.e. the investigator(s) regularly treat(s) the target population). They should also have an adequate number of qualified staff and facilities available for the foreseen duration of the study to enable them to conduct the study properly and safely.

Sites will be expected to complete a delegation of responsibilities log and provide staff contact details.

The site should have sufficient data management resources to allow prompt data return to UCL CCTU.

6.2 Site approval and activation

On receipt of the signed Clinical Study Site Agreement, Investigator Agreement, approved delegation of responsibilities log and staff contact details, written confirmation will be sent to the site PI. The study manager or delegate will notify the PI in writing of the plans for site initiation.

The site must conduct the study in compliance with the protocol as agreed by the Sponsor and, which was given favourable opinion by the Research Ethics Committee (REC) and/or Institutional Review Board (IRB). The PI or delegate must document and explain any deviation from the approved protocol, and communicate this to the study team at UCL CCTU.

A list of activated sites may be obtained from the Study Manager.

6.3 Participants

6.3.1 Eligibility Criteria

6.3.1.1 Participant selection

There will be **NO EXCEPTIONS** (waivers) to eligibility requirements at the time of recruitment. Questions about eligibility criteria should be addressed PRIOR to attempting to recruit the participant.

The eligibility criteria for this study have been carefully considered and are the standards used to ensure that only medically appropriate participants are entered. Participants not meeting the criteria should not be entered into the study. It is therefore vital that exceptions are not made to these eligibility criteria.

Participants will be considered eligible for enrolment in this study if they fulfil all the inclusion criteria and none of the exclusion criteria as defined below.

6.3.1.2 Participant Inclusion Criteria

- Age \geq 18 years;
- Singleton pregnancies;
- Live fetus at 11-13 weeks of gestation;
- Informed and written consent.

6.3.1.3 Participant Exclusion Criteria

- Women who are unconscious or severely ill, those with learning difficulties or serious mental illness.
- Pregnancies complicated by major fetal abnormality identified at 11-13 weeks of gestation

6.3.1.4 Eligibility Criteria for Individuals Performing the Interventions

All centres involved in the data collection will have staff who are appropriately trained in obstetric ultrasound and possess certificates of competence from the FMF for non-routine measurements.

6.3.1.5 Co-enrolment Guidance

For parous women, participation in the study in a previous pregnancy will be checked (as there will be a record in the electronic Source Data) in order to prevent participants from being enrolled more than once in this study. Data of each participant should only be recorded as one entry in the database.

6.3.1.6 Recruitment Procedures

Written informed consent will be obtained from all women agreeing to participate in the screening study for PE and **BEFORE** any study-specific procedures are performed for the study. The only procedures that may be performed in advance of written informed consent being obtained are those that would be performed on all participants in the same situation as part of usual standard of care, such as the routine first-trimester combined screening for aneuploidies, which includes an ultrasound scan to measure fetal CRL, NT and assessment of fetal anatomy and blood draw for measurement of biochemical markers including PAPP-A (DELFI A XPRESS analyser [PerkinElmer Life and Analytical Sciences, Waltham, USA]; BRAHMS KRYPTOR analyser [Thermo Fisher Scientific, Hennigsdorf, Germany]; Cobas analyser [Roche Diagnostics, Penzberg, Germany]).

6.4 Outcomes

6.4.1 Primary Outcomes

The primary outcome will be the false positive and true positive frequencies for screening using the Bayes theorem based method and for screening according to the NICE guidelines. The screen positive threshold applied to the risks will be determined by the NICE guidelines. It is anticipated that there will be an increase in detection rate for all-PE from 35% (NICE method) to 50% (mini-combined test), at false positive rate of 10%.

The definitions of PE were that of the International Society for the Study of Hypertension in Pregnancy [13] and the American College of Obstetricians and Gynecologists [14]. The systolic blood pressure should be \geq 140 mm Hg and/or the diastolic blood pressure should be \geq 90 mmHg on at least two occasions four hours apart developing

after 20 weeks' gestation in previously normotensive women and there should be proteinuria (≥ 300 mg in 24 hours or two readings of at $\geq 2+$ on dipstick analysis of midstream or catheter urine specimens if no 24-hour collection is available). In the absence of proteinuria, new onset of any of the following systemic findings: a) thrombocytopenia (platelet counts $< 100,000 \mu\text{L}$); b) renal insufficiency (creatinine > 1.1 mg/dL or 2-fold increase in creatinine in the absence of underlying renal disease); c) abnormal liver function (ie, hepatic transaminase levels twice normal); d) pulmonary oedema; or e) cerebral or visual symptoms. Preterm-PE is PE that requires delivery before 37 weeks' gestation.

6.4.2 Secondary Outcomes

Secondary outcome measures:

- To demonstrate an increase in detection rate for all-PE:
 - From 35% (NICE method) to 55% (combined test), at false positive rate of 10%;
- To demonstrate an increase in detection rate for preterm-PE
 - From 40% (NICE method) to 60% (mini-combined test), at false positive rate of 10%.
 - From 40% (NICE method) to 75% (combined test), at false positive rate of 10%.

Collection of pregnancy and neonatal outcomes

Data on pregnancy outcomes will be collected from the hospital maternity records or their general medical practitioners.

The obstetric records of the participating women with pre-existing or pregnancy associated hypertension will be examined to determine if the condition was chronic hypertension, PE or gestational hypertension.

6.5 Participant Timeline

Study procedure by visit:

Screening Visit (11-13 week of pregnancy or CRL 45-84mm)

- Informed Consent
- Patient demographics
- Height and Weight
- Maternal medical and obstetric history
- Family history
- Drug history including aspirin intake
- Routine first-trimester scan
- MAP
- Uterine artery blood flow (transabdominal colour Doppler ultrasound)
- PAPP-A and PIGF measurements
- Risk calculation

Follow up visit: 19-24 week of pregnancy

- Routine anomaly scan

	11-13 weeks scan	19-24 weeks scan
Gestation (weeks)	11-13 or CRL 45-84mm	19-24
Patient information and characteristics	√	
Informed consent	√	
Measurement of weight and height	√	
Measurement of MAP	√	
Fetal ultrasound scan	√	√
Measurement of uterine artery PI	√	
Measurement of biochemical markers (PAPP-A and PIGF)	√	
Risk calculation	√	
Drug history including aspirin intake	√	

Laboratory Tests

At the time of the 11-13 weeks scan, 20mL of maternal blood will be taken for the measurement of biochemical markers using either the DELFIA XPRESS analyser (PerkinElmer Life and Analytical Sciences, Waltham, USA), BRAHMS KRYPTOR analyser (Thermo Fisher Scientific, Hennigsdorf, Germany) or Cobas analyser (Roche Diagnostics, Penzberg, Germany). At sites with available storage facilities, the remaining serum and plasma will be stored at -80°C for future studies on potential biochemical markers of pregnancy complications.

6.5.1 Early Stopping of Follow-up

If a participant chooses to withdraw from the study, they should continue to be followed up according to the follow-up schedule defined in the protocol, providing they are willing. They should be encouraged not to leave the study. If, however, the participant exercises the view that they no longer wish to be followed up either, this view must be respected and the participant withdrawn entirely from the study. UCL CCTU should be informed of the withdrawal in writing using the appropriate SPREE study documentation. Unless consent for all data already collected is withdrawn it will be kept and included in analyses for all participants who stop follow up early.

Participants who stop study follow-up early will not be replaced.

6.5.2 Participant Transfers

If a participant moves from the area which is served by the hospital where they were recruited to the study, making continued follow up at their consenting centre inappropriate, every effort should be made for them to be followed at another participating study centre. Written consent should be taken at the new centre and then a copy of the participant's CRFs should be provided to the new centre. Responsibility for the participant remains with the original consenting centre until the new consent process is complete.

6.5.3 Loss to Follow-up

For participants that are lost to follow up, every effort should be made to contact their general practitioners in order to acquire the pregnancy outcomes. We will also use NHS spine to trace them by NHS number in case they change their GP.

6.5.4 Study Closure

The end of the study for individual participants will be defined as delivery of the baby/end of the pregnancy. The end of the study as a whole will be defined as the point at which the last participant (n=16,850) has fulfilled the above definition and details of their complete pregnancy outcome have been collected. This will take approximately 15 months to complete.

6.6 Sample Size

We propose to recruit 16,850 patients from at least six UK centres (Table 1). On the assumption of a 5% no follow up rate there will be 16,000 evaluable patients.

Table 1. Recruitment centres with average number of deliveries per year and anticipated number of patients that would be recruited to the study.

Recruitment centre	Average deliveries/year	Anticipated recruitment
King's College Hospital	11,000	5,100
Medway Maritime Hospital	5,500	2,600
North Middlesex Hospital	5,500	2,600
Homerton University Hospital	6,000	2,800
Southend University Hospital	3,900	1,875
University Hospital Lewisham	3,900	1,875
Total	35,800	16,850

The power properties of the primary analysis across a range of assumptions regarding the effect of aspirin were examined using computer simulations each of 100,000 trials. The power properties of the test depend on the effectiveness of aspirin and the proportions of patients treated with aspirin. The most pessimistic situation, in terms of power to detect a difference in sensitivity is where a large proportion of patients in the NICE screened positive group are treated and a small proportion in the NICE screened negative group are treated and aspirin is most effective. The power properties of the study under the most extreme case are illustrated in Table 2. The test has power in excess of 80% to detect differences of 10 percentage points.

Table 2. Power for the detection of difference in sensitivity between the index text and the comparator at the one sided 2.5% level with a sample of 16,000 evaluable patients. The figures in the body of the table are the power of the test. The margins give the sensitivity of the comparator test and the index text. It is assumed that 90% of NICE screened positive patients and 10% of NICE screened negative patients are treated with aspirin and that aspirin reduces the incidence of PE by 50%.

	Comparator									
	35%	40%	45%	50%	55%	60%	65%	70%	75%	
	35%	33.4%	85.0%	99.3%	100.0%	100.0%	100.0%	100.0%	100.0%	100.0%
	40%		32.0%	84.1%	99.2%	100.0%	100.0%	100.0%	100.0%	100.0%
	45%			31.7%	83.7%	99.1%	100.0%	100.0%	100.0%	100.0%
Index test	50%				31.8%	83.9%	99.2%	100.0%	100.0%	100.0%
	55%					31.9%	84.8%	99.4%	100.0%	100.0%
	60%						33.2%	86.5%	99.6%	99.6%
	65%							34.8%	88.7%	88.7%

6.7 Recruitment and Retention

6.7.1 Recruitment

In all the participating centres, all women attending for the routine 11-13 weeks scan will be invited to take part in the screening study for PE. Where possible, the PIS will be sent with the appointment letter to all potential participants.

Recruitment rates will be actively monitored by the SMG. This will include analyses by centre of the number of women recruited. Appropriate strategies will be implemented if recruitment falls below an acceptable level.

6.7.2 Retention

If women fail to attend their follow-up visits, the study coordinators will contact them to arrange for another visit within 7 days of the study visit window.

6.8 Data Collection, Management and Analysis

6.8.1 Data Collection Methods

Patient information for this study will be entered into an electronic CRF. The main CRF will be held electronically only and will not be printed. The CRF will be composed of 3 parts:

CRF part 1 This part will include patient demographics, medical, obstetric and drug history, family history, measurement of MAP, collection of blood samples for biochemical testing, performance of an ultrasound scan to confirm the GA by the measurement of fetal CRL and measurement of the uterine artery PI; and risk for PE. Participants will be identified on CRFs by initials, patient code and site name, date of enrolment and the enrolling site-PI or fellow.

CRF part 2 will record details of the routine clinical visits and medical, obstetric and drug history at 19-24 weeks.

CRF part 3 will record details of pregnancy outcomes, details of labour, development of PE, neonatal birth weight and outcomes.

If a participant withdraws from follow-up a paper CRF will be completed. CRFs must be kept current to reflect the participant's status at each phase during the course of the study.

The CRFs will be the source documents of the study that must be available at all times for audit.

A participant identification record will be kept by each site-PI that would allow linking of the participant study number, participant name and date of birth for those included in the study along with participant contact information. This file will be kept electronically at sites.

6.8.2 Non-Adherence and Non-Retention

For non-adherers (as defined by poor attendance to the clinical visit) we will record details of pregnancy outcomes, details of labour, development of PE, neonatal birth weight and outcomes as for adherers. Reasons for non-adherence and non-retention and those lost to follow up will be recorded in the CRF.

6.8.3 Data Management

The UCL CCTU will act as custodian for the study data. The following guidelines will be strictly adhered to:

- Patient data will be pseudo-anonymised.
- All anonymised data will be stored on a password protected UCL CCTU computer.

6.8.4 Statistical Methods

6.8.4.1 Statistical Analysis Plan

To enable the analyses to be reproduced and to produce the report in a timely way, the analysis will be programmed in R [17] in the period prior to the completion of follow up. It will be documented in a stand-alone statistical analysis plan (SAP). This will include all programmes, dummy tables and figures. The SAP will be finalised blinded to outcome data. Results will be presented according to the STARD guidelines. All data and programs will be provided to an independent statistician for evaluation.

6.8.4.2 Statistical Methods – Outcomes

The purpose of the analysis is to compare performance of screening using the Bayes theorem based method with that using the NICE criteria. The difference will be tested at the one-sided 2.5% level.

The primary analysis will be of the prospective cohort of 16,000 patients. All patients with data on maternal characteristics, medical history and outcome will be included in the analysis. Risks will be calculated using the algorithm developed. These calculations will be fully pre-specified so that the prospective cohort can be used as an independent test data set.

The essential features of our primary analysis are as follows. The NICE criteria define a high-risk group by applying a set of rules to information on Mat-CH resulting in a binary (positive/negative) outcome for each pregnancy. These results will provide an overall screen positive rate of around 10%. We will firstly determine the threshold for the risks that gives the same number of screen positives as NICE. Secondly, we shall construct the 2 x 2 contingency table of counts by classifying each patient with PE according to the result from NICE and the risk assessment (Table 3). We shall then apply an extension of McNemars test that uses the difference between the counts of discordant pairs b and c. Under the null hypothesis of equality, these counts have the same expected value. Under the alternative hypothesis of superiority of the Bayes theorem based method to NICE, the expected value of c exceeds that of b.

Table 3: Classification of cases PE according to screening results.

		Bayes method	
		+	-
NICE	+	a	b
	-	c	d

A complication for any comparative study of PE is that, by converting true positives to false positives, treatment with aspirin reduces the incidence of PE in the treated group. If treatment is dependent on screening using a particular method, then the bias will reduce the apparent DR for that method. We have therefore developed a modification to McNemars test that incorporates an assumed relative risk for aspirin and individual level data on aspirin treatment. We will be classifying individuals according to treatment with aspirin as summarised in Table 4.

Table 4: Classification of cases PE according to screening results.

Untreated		Bayes method	
		+	-
NICE	+	a_0	b_0
	-	c_0	d_0

Treated		Bayes method	
		+	-
NICE	+	a_1	b_1
	-	c_1	d_1

If aspirin reduces the incidence of PE by θ and the proportions of women in the population receiving aspirin are denoted by p_a , p_b , p_c and p_d in the cells corresponding to a, b, c and d then under the null hypothesis of no difference in DR the cell counts in Table 4 are to have expected values proportional to the probabilities in Table 5.

Table 5: Expected cell proportions according to treatment and test result.

Untreated		Bayes method	
		+	-
NICE	+	$1-p_a$	$1-p_b$
	-	$1-p_c$	$1-p_d$

Treated		Bayes method	
		+	-
NICE	+	$p_a(1-\theta)$	$p_b(1-\theta)$
	-	$p_c(1-\theta)$	$p_d(1-\theta)$

The modified test compares counts c_0+c_1 with b_0+b_1 . Under the null hypothesis of no difference in sensitivity, the expected counts is in the ratio $1-p_c\theta : 1-p_b\theta$ respectively. Note that if $p_c = p_b$ or $\theta = 1$ (aspirin is ineffective) this ratio is 1:1 and the test reduces to McNemars test. If $\theta < 1$ (aspirin reduces risk) and $p_b > p_c$ then the expected value of the counts is larger for c_0+c_1 than for b_0+b_1 and McNemars test is biased against NICE. Our approach to analysis is to take an external estimate of θ based on the best available evidence at the time to adjust the analysis for the effect of aspirin. A sensitivity analysis with respect to variations across a plausible range of θ (e.g. a 95% confidence interval) based on the evidence at the time will be presented. Point and estimates and 95% confidence estimates of DR and differences between DR adjusted for potential treatment effects will also be produced using the model described above. The primary comparison, will be a comparison between NICE and the mini combined test.

Primary comparisons are as follows:

- NICE vs. the mini-combined test for all-PE.
- NICE vs. the combined test for all-PE;
- NICE vs. the mini-combined test for preterm-PE;
- NICE vs. the combined test for preterm-PE.

Secondary comparisons are as follows:

- A. NICE vs. the Bayes risk assessment based on Mat-CH;
- B. Bayes risk assessment using Mat-CH vs. mini-combined test;
- C. Bayes risk assessment using Mat-CH vs. combined test;
- D. Mini combined test vs combined test.

For comparisons (B) – (C) a receiver operating characteristic curve (ROC) analysis, including comparison of areas under the ROC curve will be reported. All comparisons will be made with respect to all-PE and preterm-PE.

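### Section 6.8.4.2 uses θ first as a proportional reduction in PE and then as a relative risk, so the stated no-effect case of the primary test is false under its own formula

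*Protocol*

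**What the plan says.** Protocol section 6.8.4.2 adapts McNemar's test to allow for aspirin use. The test is said to be one that "incorporates an assumed relative risk for aspirin and individual level data on aspirin treatment".

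The parameter is introduced as a reduction: "If aspirin reduces the incidence of PE by θ and the proportions of women in the population receiving aspirin". Table 5 gives untreated cells as 1−p and treated cells as p(1−θ). From this the protocol derives the null ratio of expected discordant counts, c (NICE negative, Bayes positive) to b (NICE positive, Bayes negative), as (1−p_cθ):(1−p_bθ).

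The note that follows gives the no-effect case as "\theta = 1$ (aspirin is ineffective) this ratio is 1:1 and the test reduces to McNemars test", and glosses θ < 1 as "aspirin reduces risk".

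The value is not fixed: "Our approach to analysis is to take an external estimate of" θ from the best evidence available at the time, with a sensitivity analysis over a plausible range such as a 95% confidence interval. The same model is to supply the adjusted detection rates, their differences and the confidence intervals.

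**The concern.** The definition, Table 5 and the ratio make θ a proportional reduction, 1−RR. The two remarks after the ratio make it a relative risk. The scales run in opposite directions: no effect is 0 on the first and 1 on the second. The formula and the stated no-effect case therefore cannot both hold.

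This matters because the ratio is the null hypothesis of the primary comparison. Treatment-effect evidence is usually published as a relative risk with a confidence interval, and no sentence says that it must be converted before it enters the formula. Entering it unconverted would turn the adjustment round: the weaker the effect of aspirin, the larger the correction. The sensitivity analysis over θ would run in the wrong order too. A reduction below 50% would be over-adjusted, costing power; one above 50% would be under-adjusted, inflating type I error.

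**Working it through.** **Inputs from the protocol.** Aspirin uptake p_b = 0.90 (NICE positive) and p_c = 0.10 (NICE negative), and a 50% reduction, from Table 2 (section 6.6). A reduction of about 10% and PE prevalence of about 2%, from section 5.1. 16,000 evaluable women (section 6.6). Detection rates of 35% and 50% (section 6.4.1). One-sided 2.5% level (section 6.8.4.2).

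**Assumptions.** The 60% reduction, the milder uptakes of 50%/5% and 30%/3%, and the correlation between the tests among PE cases.

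**1. The protocol's own figure.** Ratio c:b = (1−p_cθ)/(1−p_bθ).
- θ = 1: (1−0.10)/(1−0.90) = 0.90/0.10 = 9. The stated 1:1 is not reproduced.
- θ = 0: 1/1 = 1. The ratio is 1:1 here, or whenever p_b = p_c.

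**2. Null ratio if a relative risk is entered as θ (uptake 90%/10%).**

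| True reduction | Correct, θ = reduction | RR entered as θ |
|---|---|---|
| 10% | 0.99/0.91 = 1.09 | 0.91/0.19 = 4.79 |
| 50% | 0.95/0.55 = 1.73 | 0.95/0.55 = 1.73 |
| 60% | 0.94/0.46 = 2.04 | 0.96/0.64 = 1.50 |

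The readings agree only at a 50% reduction, where the reduction and the relative risk are the same number.

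**3. Model for the consequences.** Untreated-equivalent PE cases: 16,000 × 0.02 = 320. Discordant counts are Poisson with means 320·b·(1−p_b·r) and 320·c·(1−p_c·r). Here r is the true reduction, and b and c are the discordant proportions given by a bivariate normal latent correlation. The test is a one-sided 2.5% normal-approximation test of c/(b+c) against ratio/(1+ratio).

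The protocol does not give the correlation, so I compared the model with Table 2 (r = 0.5, uptake 90%/10%):

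| Comparison | Table 2 | Independent tests | Correlation 0.74 |
|---|---|---|---|
| 35% vs 45% | 85.0% | 56% | 86% |
| 35% vs 50% | 99.3% | 88.5% | 99.6% |

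Independence does not fit Table 2. A correlation of about 0.74 roughly does, and is used below.

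**4. Consequences if the RR were entered unconverted (correlation 0.74).**

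| Uptake, NICE+/NICE− | Power, 35% vs 50%, 10% reduction | Type I error, 35% vs 35%, 60% reduction |
|---|---|---|
| 90%/10% (Table 2) | about 0.5% | about 16% |
| 50%/5% (assumed) | about 89% | about 6.5% |
| 30%/3% (assumed) | about 99% | about 4.3% |

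With θ entered correctly, power exceeds 99% in all three rows, and type I error is at or slightly below the nominal 2.5%.

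The correlation matters as well. At 90%/10% uptake and a correlation of 0.5, the unconverted entry gives power of about 0% and type I error of about 21%.

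**The case against.** The strongest reply is that the operative specification is consistent. The definition, all four treated cells of Table 5 and the ratio use one scale, and the ratio follows from the table. Only two parenthetical remarks are off. A careful statistician would see the intention, and the statement that plain McNemar is biased against NICE when p_b > p_c is right in direction for any real benefit of aspirin. All of this stands. It limits the point to a misstatement, but does not remove it: the remark about θ = 1 is the one check that the protocol offers on the formula, and the formula fails it.

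There are also safeguards. Section 6.8.4.1 promises a stand-alone SAP that holds the programs and is finalised blinded to outcome, with data and programs passed to an independent statistician. Section 6.9.1 says that the independent statistician on the SSC will review the SAP. These make an uncaught error less likely, but a checker working from this text would find support for two null values.

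A reader might infer more than the protocol supports:
- **That the analysis will be run wrongly.** The SAP and code are not at hand. The figures above are conditional on an unconverted entry.
- **That the power work was blind to the problem.** This is true of the printed Table 2, which uses a 50% reduction. Section 6.6, however, says that the simulations covered a range of assumptions about aspirin's effect.
- **That the sentence on an assumed relative risk is a further contradiction.** It is not: the multiplier 1−θ in Table 5 is the relative risk.
- **That an unconverted entry would nearly always produce a significant result in favour of NICE.** For a 10% reduction at 90%/10% uptake, independent tests do give this in over 99% of runs, but independence does not fit Table 2. At a correlation of 0.74 it is about 10%.
- **That 90%/10% is the expected uptake.** Section 6.6 presents it as the extreme case, and section 5.3 expects adherence to vary.

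**Conclusion.** Section 6.8.4.2 contradicts itself in the text that sets the primary null hypothesis. This part is algebra and needs no outside assumption: at θ = 1 the printed ratio is (1−p_c):(1−p_b), which is 9:1 at the Table 2 uptake and not 1:1.

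What follows is a risk and not a demonstrated error. If a relative risk were entered unconverted, the damage would run from small to decisive. Across the three uptakes shown, power would be between about 99% and 0.5% for a 10% reduction, and one-sided type I error between about 4.3% and 16% for an assumed 60% reduction. These ranges rest on the assumed correlation of about 0.74 and on uptakes of which only 90%/10% is in the protocol. The sample size, Table 2 and the stated direction of the McNemar bias are unaffected. The text should still be corrected, because the value and the scale of θ are both left open.

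**What to change.** Keep Table 5 and the ratio. Define θ explicitly as 1−RR, and change the two remarks to θ = 0 for an ineffective aspirin and θ > 0 for a reduction in risk. State that an external relative risk and both of its confidence limits are converted to 1−RR before use in the test, the adjusted detection rates and the sensitivity analysis. Add a check that the R code returns 1:1 at RR = 1.

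An equivalent alternative is to work in RR throughout, with treated cells p·RR and null ratio [1−p_c(1−RR)]:[1−p_b(1−RR)].

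The cost is a few words in the protocol, the same definition in the SAP, and one code check. Participants, data collection and sample size are not affected.
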